**Randomized Clinical Trial (RCT) protocol**  
**5/30/2023**

**Principal Investigator (PI):**  
**[name], MS**

**NCT 04288115**

**Aim. Evaluate the feasibility of LT4 discontinuation among Veterans with SCH and determine the changes in quality-of-life measures, treatment burden, and adverse events.**

Design: Double-blind, placebo-controlled randomized clinical trial

Performance site: CAVHS

Participants: Fifty veterans with LT4-treated SCH will be randomized to either (1) continue current dose of LT4 [pre-study dose] or (2) placebo. Up to 150 veterans will need to sign consent and HIPAA authorization to reach 50 randomized participants due to the anticipated screen failure rate. The screen failure rate accounts for participants whose baseline lab results (TSH, FT4 and LDL) are out of study range. Participants will be identified from CDW/Strategic Management (Aim 1) and referrals from CAVHS providers (including Primary Care or Endocrine clinic providers).

Exclusion Criteria: (1) TSH > 10 mIU/L (at any point), (2) LT4 dose more than 75 mcg daily, (3) use of antithyroid medications, amiodarone, tyrosine kinase inhibitors or lithium, (4) history of thyroidectomy or radioactive iodine therapy, (5) LT4 suppressive therapy for thyroid cancer, goiter or inflammation, (6) pregnancy or plans for pregnancy in the next 6 months, (7) an unstable medical condition that would jeopardize safety or interfere with study participation, (8) hospitalization for major illness within the previous 4 weeks, (9) severe hypothyroidism-related symptoms, (10) strong family history of hypothyroidism, (11) severe dyslipidemia, (12) acute coronary artery syndrome, acute myocarditis, or pancarditis or stroke within the previous 12 months, (13) Grade IV New York Heart Association (NYHA) heart failure, (14) receiving services from hospice, (15) lack of decision-making capacity, (16) terminal medical condition for which life expectancy would be less than 6 months, (17) not willing to stop LT4, (18) self-reported non-adherence to LT4 therapy and (19) abnormal TSH at time of screening for participation (assessed during Baseline Visit). Pregnancy testing will be performed for females of child-bearing potential that sign consent to participate in the study. The results will be reviewed prior to randomization.

Recruitment: We will send an **IRB-approved opt-out letter** to eligible veterans identified from CDW/Strategic Management or referral from CAVHS provider. The Principal Investigator (PI) has presented the study background, goals, and procedures to endocrinologists and primary care clinicians at CAVHS, answered questions, and got feedback from them (Development phase). A post-presentation poll of primary care physicians showed that 75% felt that LT4 discontinuation was acceptable in patients with SCH and 97% were comfortable with randomization of their eligible patients in the study. All endocrinologists felt that LT4 discontinuation was acceptable in patients with SCH and were comfortable with randomization of their eligible patients in the study. Clinicians were informed that Veterans under their care may be invited to participate and that those Veterans may want to discuss participation with their clinicians prior to enrolling. Before beginning to recruit, we will repeat the presentation to CAVHS clinicians who might prescribe LT4, including primary care, medicine, and endocrinology service clinicians, to refresh their memories and ensure that we reach clinicians new to CAVHS. In addition, an email with materials describing the study will be sent to clinicians who miss the presentation. Clinicians will be invited to contact the PI if they have questions or concerns about the study. The PI will utilize the Medicine and Primary Care quarterly conference to update clinicians. Study staff will send up to 100 IRB-approved opt-out letters weekly until all eligible veterans identified are sent the letter or 50 veterans are randomized (whichever occurs first). The pool of potential participants will be identified from CDW/Strategic Management and referrals from CAVHS providers. Women and minorities will be included in the study in proportion to their presence among CAVHS patients. We will submit and get approval for a **telephone script**. The designated study staff will call potential participants, with varying lengths of LT4 therapy, that do not opt-out (after at least two weeks from the mail date of the opt-out letter) and use the IRB-approved telephone script to guide the conversation.

Consenting: Written ICF and HIPAA will be obtained by the designated study staff prior to any study activities.

Intervention: (1) Continue current dose of LT4 [control or “sham discontinuation”] or (2) placebo [intervention or “real discontinuation”]

Randomization Scheme: 1:1, a randomized block design will be implemented to ensure group sizes are equal. Block sizes of 2, 4, and 6 will be used. In addition, randomization will be stratified by participant's pre-study dose of LT4.

Blinded Person(s): PI, Co-Investigators (Drs. [name], [name]), Research Coordinator/Study Staff (SC), Participant, participant's other clinicians (routine care), Biostatistician, Safety Monitor

Unblinded Person(s): [name] (Co-Investigator and Research Pharmacist), [name] (Research Staff and Research Pharmacy), [name] (Research Staff and Pharmacist)

Study Medication Blinding Procedure: The brand of LT4 to be used in this study will be Synthroid® tablets of 25 mcg, 50 mcg, and 75 mcg (AbbVie Inc). The study drugs (LT4 and placebo) will be sourced, assembled, and packaged by the CAVHS Research Pharmacy. Over-encapsulation will be achieved using a capsule filler and will ensure that capsules are kept as small as possible for the ease of swallowing (DB capsules gelatin size AA, color: White Opaque, manufacturer: Capsugel).

Study Medication Dosing: Participants will be instructed to start the study medication the day after randomization. The study medication will be taken orally once a day. A two-month supply of study medication will be provided to the participant at (1) Baseline, (2) around the time of Clinic Follow-up 1, and (3) around the time of Telephone Visit 3 (Month 4). Study medication may also be provided (in-person or by mail) at an unscheduled visit for reasons such as loss of study medication or resupply.

Source of Information: CAVHS veterans

Use of Information: Evaluate the feasibility of LT4 discontinuation among veterans with SCH and determine changes in quality-of-life measures, blood lipids and adverse events.

Data Collected: (1) **Baseline Visit:** ICF, HIPAA, medical history, demographics, Vital signs (blood pressure and pulse, height and weight), study questionnaires (ThyPRO Hypothyroid symptoms and Tiredness scales, EQ-5D ThyPRO-39) and blood sample collection (TSH, FT4, lipids). (2) **Telephone Visit 1** (Month 1 +/- 3 days): Adverse event assessment and study medication compliance assessment. (3) **Clinic Follow-up 1** (6-8 weeks post randomization): Vital signs (blood pressure and pulse, weight), study questionnaires (ThyPRO Hypothyroid symptoms and Tiredness scales, EQ-5D), study medication compliance assessment, adverse event assessment and blood sample collection (TSH, FT4, TPO antibodies). (4) **Telephone Visit 2** (Month 3 +/- 3 days): Adverse event assessment and study medication compliance assessment. (5) **Telephone Visit 3** (Month 4 +/- 3 days): Adverse event assessment and study medication compliance assessment. (6) **Telephone Visit 4** (Month 5 +/- 3 days): Adverse event assessment and study medication compliance assessment. (7) **Clinic Follow-up 2** (Month 6 +/- 3 days): Vital signs (blood pressure and pulse, weight), study questionnaires (ThyPRO Hypothyroid symptoms and Tiredness scales, EQ-5D, ThyPRO-39, End of Study survey), study medication compliance assessment, assessment of integrity of blinding, disclosure of study medication assignment to participant, blood sample collection (TSH, FT4, blood lipids), duration of LT4 therapy and return to usual care plan. (8) **Unscheduled Visit:** an unscheduled visit(s) may be performed during the study. The unscheduled visit may be completed by telephone or in-person. Possible reasons for an unscheduled visit include safety assessment (such as lab collection for assessment of possible adverse event), repeat lab collection (test error or result confirmation), early termination (participant, Investigator, or joint decision) and/or study medication resupply.

Planned Analysis: Initial data analysis will include descriptive statistics for all variables, including assessment of potential outliers and the extent of missing data. If the missing data rate is small, < 5%, and found to be at random, then complete case analyses will be performed; otherwise, multiple imputation strategies will be explored. Data will be presented as frequencies for categorical variables and means (standard deviations) for continuous variables. We will compare characteristics between groups using t-tests for quantitative variables and chi-square tests for categorical variables. For the primary outcome, intervention feasibility, we will calculate participants' willingness to enter the trial (percent of eligible Veterans approached who consented to participate), recruitment rate (number of patients randomized divided by the length of the recruitment period, i.e., from the date that recruitment opened to the date of the last randomization). These measures will shed light on the anticipated acceptability of LT4 discontinuation. Finally, we will calculate completion rate for each arm. Secondary outcomes include changes from baseline to 6 months in the ThyPRO Hypothyroid Symptoms and Tiredness scores, EQ-5D, ThyPRO-39 and blood lipids. We will also assess changes in weight, body mass index, blood pressure,

and pulse. Analysis of covariance (ANCOVA) models will be employed to analyze these outcomes. Baseline measures and gender will be included in the models as covariates. A one-sided t-test will be used to determine whether the mean ThyPRO Hypothyroid Symptoms and Tiredness scores for the real discontinuation group differ from the mean ThyPRO Hypothyroid Symptoms and Tiredness scores of the sham discontinuation group by no more than 14 points. An  $\alpha$ -level of 0.05 will be used to determine the statistical significance of the non-inferiority test for each ThyPRO domain. Failure to reject the null hypothesis will suggest that the QoL measures in the real discontinuation group, on average, are more than 14 points worse than in the sham discontinuation group. This will be considered as evidence against our conjecture that discontinuation does not negatively affect the QoL of patients with SCH. In addition, analyses comparing groups with respect to adverse event rates will be performed using chi-square tests. Analyses will be based on the intention-to-treat principle. Statistical analyses will be done using SAS 9.4 (SAS Institute, Cary, NC).

*Additional details Analysis Plan:* We will add a Biostatistician to the project. They will be hired through an IPA to work on the project. The Biostatistician will be sent the data set by encrypted email and will use computer software on their laptop (non-VA) to complete the analysis. No name, date of birth or SSN will be included in the data set for analysis. Those data points will remain within the VA protected environment.

*Sample size estimates:* The overarching goals of this pilot trial are to assess the feasibility of a subsequent, full-scale effectiveness trial and to obtain preliminary estimates of effect sizes. Thus, the pilot needs to be large enough to be informative about the feasibility of recruitment/retention and research procedures and to provide enough information on the efficacy of the intervention to justify and inform the planning of a full-scale trial. The primary endpoints of the full-scale RCT will be the ThyPRO Hypothyroid Symptoms scale and Tiredness scale scores. With an estimated standard deviation of 20 for ThyPRO hypothyroid scale score, from a study of patients with autoimmune hypothyroidism, a sample size of 23 Veterans per group will allow us to achieve 80% power using a 5%  $\alpha$ -level to determine statistical significance for a one-sided t-test; accounting for a drop-out rate of less than 10%, a final sample size of 50 patients will be required. This sample size is adequate both to assess feasibility and to obtain preliminary data on effect sizes.

*Participant Compensation:* Participants will be provided compensation for time and travel expenses as a result of participating in the study. The payments will be distributed as follows: (1) \$50 for completion of Baseline Visit, (2) \$50 for completion of Clinic Follow-up 1 (Month 2), (3) \$50 for completion of Clinic Follow-up 2 (Month 6), and (4) \$100 for completion of all study activities and End of Study survey. The participant will be paid within 4-6 weeks after each clinic visit. Payment will be issued by check or by electronic transfer of funds according to local medical center procedures. The participant name, SSN, address and date of visit are required to process the funds. An Internal Revenue Service (IRS) Form 1099 will be generated using the participant's SSN. On a case-by-case basis, the PI may authorize additional compensation to cover the cost of transportation (public transportation or gas mileage estimate).

*Compliance and Withdrawal:* We will provide an **IRB-approved pill diary** to all study participants. The study team will assess study medication compliance throughout the study. The pill diary may be reviewed at the follow-up clinic visits. Study medication compliance will be considered good if the participant reports taking study medication 80-100% of the time. **Participants may decide not to continue the study medication (LT4 or placebo) at any time. Additionally, the PI may decide not to continue the study medication for an individual (for example, following lab results). We will assist the participant to ensure that appropriate medication, if any, is started at the time of study medication discontinuation. If this occurs, the participant will be asked if they will continue the study (including follow-up visits, blood collection and study questionnaires) without continuing the study medication. If the participant agrees, they will be followed per protocol. If the participant does not agree, they will be classified as withdrawn from the study. We will document this occurrence, reason for discontinuation of study medication and participant decision to continue participation in the study (visits, blood collection and study questionnaires). Participants may agree to all or some of the study procedures.** We will instruct participants who discontinue the study

medication to dispose of any unused study medication in the manner in which they usually dispose of expired medications or offer to have them return the unused study medication to CAVHS. Participants may withdraw from the study at any time. Withdrawal by the participant will be defined as any participant that informs the study team that they do not wish to continue the study medication, do not wish to allow any further collection of data, and do not wish to have any further contact with the study team. If they do so, they will be considered withdrawn voluntarily from the study. We will document the circumstance(s) and reason(s) for participant withdrawal. The PI may also withdraw participants from the study. This may occur in the event of inter-current illness, adverse events, protocol violations, non-compliance, or administrative reasons. We will assist the participant to ensure that appropriate medication is started at the time of withdrawal. We will instruct participants who withdraw (or are withdrawn) from the study to dispose of any unused study medication in the manner in which they usually dispose of expired medications or offer to have them return the unused study medication to CAVHS. Participants withdrawn from the study will not be replaced. To avoid breaking the blind, results of Visit 1 (Month 2) laboratory tests will not be published in CPRS but will be recorded in the Veterans Information Systems and Technology Architecture (VISTA), which is not used by clinicians for lab review. These lab results will be reviewed by Unblinded Personnel.

**Randomization Lab Criteria:** Baseline lab results (TSH, FT4 and lipid profile) will be reviewed prior to randomization by the Investigator or SC. To qualify for randomization, TSH and FT4 must be within normal reference range and LDL must be  $\leq 190$  mg/dL. Normal reference range for TSH: 0.54 – 5.6 mIU/mL. Normal reference range for FT4: 0.47 – 1.41 ng/dL.

**Study Medication Discontinuation Criteria:** The Unblinded Personnel will notify Blinded Study Personnel (SC) if a participant develops OH or hyperthyroidism. At which point, the SC will be unblinded. Results will be communicated to participants and treating physicians by Unblinded Study Personnel and/or SC. The participant will be followed per protocol (following discontinuation of study medication) unless they decide to withdraw from the study at the time of study medication discontinuation. Lab criteria for study medication discontinuation: (1) TSH  $> 10$  mIU/mL or (2) TSH  $< 0.34$  mIU/mL or (3) FT4  $< 0.47$  ng/mL or (4) FT4  $> 1.41$  ng/mL. Study medication will be discontinued if any of the criteria are met. Unblinded Study Personnel will maintain a document for each participant with the Month 2 lab results. The document details the criteria for study medication discontinuation and process of notification. The document will be stored in the Unblinded Study Personnel binder in the Research Pharmacy office (a locked, private office) inside the Outpatient Pharmacy area (locked, private area). The SC will collect a copy of the document from Unblinded Study Personnel once the participant completes the study. The copy will be maintained in the participant folder in a locked file cabinet in a private office. The PI will not be alerted to study medication discontinuation. She may inadvertently become aware of study medication discontinuation, but she will not be informed of the reason (hypothyroidism or hyperthyroidism at Month 2) in order to maintain the blind through the planned analysis. Study medication may also be discontinued in the case of early termination (participant decision to withdraw, Investigator decision to withdraw or joint decision). In this case, the PI may be alerted to study medication discontinuation and study medication assignment.

**Safety Monitor:** A safety monitor (CAVHS provider) will be designated for the project. They will serve in the dual role of Safety Monitor and Pharmacy Compliance Monitor. A log will be maintained on the S drive detailing adverse events, including occurrence of hypothyroidism or hyperthyroidism at Month 2. The log will be completed by the SC. The Safety Monitor will be granted access to the log on the S drive. They will monitor for occurrence of significant adverse events at pre-specified timepoints (at least monthly) and ensure that the pharmacy is properly conducting the study per protocol. Scheduled monitor visits will be recorded and documented in the pharmacy regulatory binder.

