There is a physical risk from blood collection. We plan to collect blood for research purposes three times during the study. We may collect additional blood, if needed, for safety assessment or repeat lab. The amount of blood collected will not exceed 17 mL per study collection. Possible risks of a blood draw include pain, bruising and/or infection, nausea, dizziness, and syncope. Both discomfort and bruising should disappear in a few days. The blood sample will be collected in the CAVHS Outpatient Lab in accordance with best practices to minimize any risks of possible adverse events. All personnel involved in the testing of blood samples will follow all needed safety and data security protocols. The risk associated with the blood collection for research purposes is not greater than the usual risk associated with standard of care.

There is a psychological risk that may be associated with the collection of quality-of-life information from RCT participants. The Veterans may be unaware of the extent to which they are experiencing symptoms, such as depression or memory loss. However, the study questions are similar to those encountered in clinical care and we have sought to use only the necessary measures that would have relevance for the participants. The questionnaires are self-administered, and the participants can skip questions that make them uncomfortable.

The clinical trial will be double blinded. Participant blinding to treatment allocation will be ensured through use of matched capsules for LT4 and placebo. However, when participants complete the clinical trial, they will be informed of whether they were allocated to LT4 or placebo and will be advised to discuss this with their usual (non-study) clinicians. In addition, there will be immediate response to requests for unblinding from clinicians if needed for optimal clinical care. A CPRS Research Note will have been written by the research coordinator describing the study procedures and listing emergency contact information. In the event that unblinding is needed for optimal clinical care, an attempt will be made to maintain blinding of the research team.

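### Assignments and Month 2 thyroid results are released participant by participant, and nothing says how the PI and the coordinator stay blind until the analysis

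*Combined protocol and SAP*

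**What the plan says.** **Who is blinded.** The Blinded Person(s) entry names the PI, two Co-Investigators and "Research Coordinator/Study Staff (SC), Participant, participant's other clinicians (routine care), Biostatistician, Safety Monitor". The unblinded list contains only pharmacy personnel, one of whom is a "Co-Investigator and Research Pharmacist".

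**When assignments are released.** Data Collected, item 7 (Clinic Follow-up 2, Month 6) lists "assessment of integrity of blinding, disclosure of study medication assignment to participant, blood sample collection (TSH, FT4, blood lipids". Safety Considerations repeats the timing: "when participants complete the clinical trial, they will be informed of whether they were allocated to LT4 or placebo". Neither place names who discloses.

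**When the Month 2 results are released.** Study Medication Discontinuation Criteria keeps each participant's Month 2 results in a pharmacy binder, then adds: "The SC will collect a copy of the document from Unblinded Study Personnel once the participant completes the study".

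**What the blind is meant to achieve.** The same section withholds from the PI the reason for a laboratory-driven stop "in order to maintain the blind through the planned analysis". For unblinding needed for clinical care, Safety Considerations promises an attempt to keep the research team blind. There is no matching sentence for the routine Month 6 disclosure.

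**Randomization.** The scheme is 1:1. "Block sizes of 2, 4, and 6 will be used. In addition, randomization will be stratified by participant's pre-study dose of LT4".

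**The concern.** The protocol takes care over the rare routes to unblinding (a laboratory-driven stop, a clinician's request) and is silent on the one that reaches every participant who completes. With release at individual completion, knowledge of assignments can build up in the study team during the trial.

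Three things are exposed:

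- **Judgements on participants still in follow-up.** The PI or a designated Investigator rates seriousness, causality and expectedness. The PI may also stop study medication or withdraw a participant. Adverse event rates and completion by arm are both reported, so these judgements feed results.
- **Analysis choices not yet fixed.** Planned Analysis leaves open the handling of outliers, whether missing data are few and random enough for complete cases, and which imputation to use. The protocol specifies neither coded arms nor a database lock.
- **Prediction of other arms.** Blocks are balanced within dose strata and their sizes are printed in the protocol, so known assignments carry some information about unknown ones.

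**Working it through.** **Setting the provisions side by side**

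| Provision | Where | Effect on the blind |
|---|---|---|
| PI, SC and Biostatistician blinded | Blinded Person(s) | Sets the aim |
| PI's blind to last through the analysis | Study Medication Discontinuation Criteria | Sets how long, in the context of Month 2 stops |
| Assignment told to participant at Month 6 | Data Collected, item 7; Safety Considerations | Rolling release, discloser not named |
| SC collects Month 2 document at completion | Study Medication Discontinuation Criteria | Rolling release of TSH and FT4 to a role listed as blinded |
| Attempt to keep the team blind | Safety Considerations | Covers clinically needed unblinding only |
| Weekly PI and staff meetings, minutes to all study staff | Data Management | No rule keeps assignments out |

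The fourth row is a stated rule, not merely a missing detail. The Month 2 document suggests the arm rather than stating it. The third row is a gap.

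**How far the blocks let staff guess other arms**

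The plan gives no figure, so there is none to reproduce.

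Inputs from the documents: 50 randomized, 1:1, blocks of 2, 4 and 6, stratified by dose, disclosure at Month 6. Assumed, because not stated: block sizes equally likely; 1, 3 or 5 equally likely strata; uniform accrual over 6, 12, 24 or 36 months; disclosure at exactly 6 months; a guesser who sees every disclosure and knows enrolment order and stratum.

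*Step 1, upper end.* Suppose every earlier member of the stratum is known and one guesses the arm that is behind. The expected number of correct guesses in a block of size 2m is m + (4^m / C(2m, m) − 1)/2.

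- Size 2: 1 + (4/2 − 1)/2 = 1.50 of 2 = 75%
- Size 4: 2 + (16/6 − 1)/2 = 2.83 of 4 = 71%
- Size 6: 3 + (64/20 − 1)/2 = 4.10 of 6 = 68%
- Equal use of the three: (1.50 + 2.83 + 4.10)/12 = 8.43/12 = 70%

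*Step 2, allowing for the six-month lag.* The probability of each arm was updated through the sequence in 400 simulated trials per scenario. The entries are the mean probability that the best guess is right (chance = 0.50), with the range over 1, 3 and 5 strata.

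| Accrual | At enrolment | Month 2 | Own Month 6 visit |
|---|---|---|---|
| 6 months | 0.500 | 0.500–0.501 | 0.685–0.700 |
| 12 months | 0.500–0.506 | 0.500–0.519 | 0.685–0.700 |
| 24 months | 0.500–0.535 | 0.501–0.561 | 0.685–0.700 |
| 36 months | 0.501–0.561 | 0.507–0.587 | 0.685–0.700 |

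At the Month 5 call, with 12 to 24 months' accrual and 1 or 3 strata, the figure is 0.52–0.62. At a participant's own Month 6 visit, 56–59% can be guessed with probability 0.70 or more, but only about 4% with certainty. The 70% of Step 1 therefore describes the moment just before that participant's own disclosure, not the follow-up as a whole.

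**The case against.** The strongest reply is that a missing detail is not a broken blind. Much of it stands.

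- **Who discloses.** A reader might infer that blinded staff run the Month 6 visit and disclose there, so that the blind cannot hold. The documents do not say so. Item 7 names no actor, unblinded pharmacy staff exist, and they already communicate thyroid results to participants and physicians, with or instead of the SC. The PI could be shielded and the Biostatistician given coded arms. The protocol specifies neither.
- **What was promised.** The aim of a blind through the analysis is stated for the PI and about the reason for a Month 2 stop. The SC is unblinded by design when a participant meets the thyroid criteria. This narrows the conflict. It does not explain why the SC needs every other participant's document before the analysis.
- **Who judges.** A reader might infer that the SC rates causality. The protocol gives that to the PI or a designated Investigator, and the SC reports events.
- **What can be biased.** The primary outcome is feasibility. The questionnaires are self-administered by participants who are still blind, provided disclosure comes after them; item 7 lists it later but does not state a time order. Selective recruitment is also tempting to infer, but letters go out until all identified eligible veterans have been sent one or 50 are randomized, and guessing at enrolment is near chance.

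What is left is the unprotected routine release, the SC's document collection, and the PI-judged and analysis decisions.

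**Conclusion.** The concern holds as a gap in protection, with one stated rule that works against the blind. Release is rolling, and no provision keeps the PI and SC blind after it. This sits badly with the list of blinded roles and with the aim stated for the PI. That conclusion rests on the text alone.

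The documents do not show that the blind will fail, nor that the arms of participants in active follow-up can be predicted about 70% of the time. Prediction is a secondary matter: 0.50–0.56 at enrolment, 0.50–0.59 at Month 2 and about 0.70 only at the participant's own Month 6 visit. These figures depend on the assumed accrual, strata and block mix, and on a guesser who sees everything, which favours prediction.

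The change should be made because it is cheap and protects adverse event causality, discretionary stops and withdrawals, and the open analysis choices. It does not put the feasibility aims in doubt.

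**What to change.** 1. **Data Collected, item 7, and Safety Considerations.** State that the already-unblinded pharmacy staff give the assignment to the participant and usual clinician, by call or letter, after the Month 6 questionnaires, vital signs and blinding assessment are recorded. State that they also supply what the plan for return to usual care needs.
2. **Study Medication Discontinuation Criteria.** Move the SC's routine collection of Month 2 documents to after database lock. Withhold routine assignments from the PI, the blinded Co-Investigators and the SC until then. The pharmacist Co-Investigator is unblinded and not covered by this. The protocol names no lock, so one sentence should define it.
3. **Leave unchanged** the existing routes for thyroid safety notification and early termination, and emergency unblinding under Safety Considerations.
4. **Randomization Scheme.** Keep the block sizes out of documents held by blinded staff.

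Routine disclosures would then tell the blinded team nothing about other arms, and prediction from them returns to 0.50. The retained safety routes could still reveal individual assignments, as the protocol already accepts.

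The cost is protocol wording and one short call or letter for each of up to 50 participants. The small downside is that disclosure does not come from the study team.
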